CLINICAL TRIALS INFORMATION:

Title: Investigating the Neural Systems That Support the Beneficial Effects of Positive Emotion on Stress Regulation

Protocol ID: 1606445

NCT Number: NCT04496258

Date of Document: 06/29/2023

ASSOCIATED PUBLICATION: The Future of Immersive Mood Induction in Affective Science: Using Virtual Reality to Test Effects of Mood Context on Task Performance

- DOI: [10.1007/s42761-023-00213-1](https://doi.org/10.1007/s42761-023-00213-1)

Procedures

Participants came into the lab for one in-person session. Prior to starting the experimental procedures, participants completed informed consent. All procedures were approved by the University of Denver's Institutional Review Board. Participants then completed task training, a practice run of the task in the VR headset, the task itself and then individual difference measures. Participants were then debriefed and compensated for their time.

Materials

Baseline and Post-Experiment Mood Ratings

Before putting on the VR headset and at the end of the experiment, participants used the modified Differential Emotions Scale (mDES; Fredrickson, 2013; Izard, 1977) to rate their current mood. We defined the mDES as a mood measure because it was intended to measure participants' current mood absent of a stimulus intended to evoke an emotional response (Rosenberg, 1998). The mDES consists of 20 questions and is comprised of two sub-scales for positive and negative emotions with 10 questions for each subscale respectively. Scales are comprised of summing all positive scores together and all negative scores together. In our study, participants were asked to rate their current experience of all 20 emotions on a five-point Likert Scale (1 – not at all to 5 – Extremely).

Mood Induction via VR

The virtual environments consisted of a beach scene and an office scene, which were shown to elicit incidental positive and neutral states respectively in our previous studies (see Song et al., 2019). The virtual environments and task were programmed with WebVR (an HTML framework) and JavaScript and displayed with a mounted VR headset (Oculus Rift) that included audio. Participants were instructed to explore the VR for approximately three minutes before the task started. Participants completed the task while still in the VR and while the virtual environments continued to play in the background. The task was programmed such that the images and instructions would appear in the center of the participant's vision regardless of their position in the VR environment.

Post Mood Induction Mood Ratings

After the three minutes of exploring the VR environment, a mood rating scale appeared in front of the participants while still immersed in the environment. Participants were told they would be using a joystick similar to a laser pointer while immersed in the VR environment. Examiners showed the participants the joystick prior to entering the VR and explained how to hold the joystick and make ratings. They were instructed to point at the rating when it appeared in front of them and use their index finger to press a trigger on the joystick to make the rating they wanted. Participants rated how positive (1: not positive at all – 9: very positive) and negative they felt (1: not negative at all – 9: very negative). The mood ratings were displayed for 5s each to account for a potential delay in participants' ratings after exploring the VR environment.

Reappraisal Task and Emotion Ratings

At the beginning of the experiment, participants were trained on the reappraisal task and given instructions about the various trial types (i.e., the look and decrease instructions), and the emotion ratings. During the look instruction, they were told to view the image in front of them and "let yourself react naturally." When given the decrease instruction, they were told to "change your emotions to decrease how negatively you feel about the picture ... reinterpret, or re-frame, or reconsider the meaning of the picture so that it makes you feel a lot more positively or a lot less negatively." The experimenter provided participants with feedback and examples of reappraisals for the decrease instruction. Participants were also instructed on the timing and method for making their emotion ratings inside the VR headset. We defined the ratings participants made after viewing the images as emotions ratings, given we were asking them to rate their emotional response to a stimulus (Rosenberg, 1998). At the end of training, participants were asked to repeat the task instructions in their own words to ensure

they fully comprehended the task. Participants then completed practice trials within the VR headset. Practice trials were intended to give participants experience with the pacing of the task within the VR headset, and practice using the joystick to make ratings.

For the task, participants first saw a cue (2s) then an instruction (3s each) and then the target neutral or negative image (7s each). Participants then rated their positive and negative emotion (3s each) on a scale from 1 (not at all positive/negative) to 9 (very positive/negative). For analyses the positive and negative ratings were (separately) averaged within each trial type for each participant. Therefore, the task constituted a 3×2 mixed factorial design: positive mood context: look-negative, look-neutral, decrease-negative – neutral mood context – look-negative, look-neutral, decrease negative.

The trials were organized into a single block which included a total of 54 images. The images were selected from the International Affective Picture System (IAPS; Lang et al., 2008). Neutral and negative pictures were selected based on the normative ratings available with the stimulus set, which include ratings of valence and arousal on nine-point scales of “1” (low pleasure, i.e., negative) to “9” (high pleasure, i.e., positive) and “1” (low arousal) to “9” (high arousal), respectively. The following distribution was used across condition type: one third look-negative, one third look-neutral, and one third decrease-negative. The images were counterbalanced with instruction type to control for the possibility that certain pictures might have had a greater impact on affect than others. Thus, participants were randomly assigned both to the positive or neutral VR mood context as well as image set. The entire task including the three-minute mood induction was completed in approximately 23 minutes.

Post-Task Individual Difference Measures and Mood Ratings

After the reappraisal task was completed, participants completed a battery of individual difference measures, including general demographics (e.g., age, gender, race) and other individual difference measures of emotion, well-being, and mental health symptoms. Participants also completed the Igroup Presence Questionnaire (IPQ)(Schubert et al., 2001) which is a measure of one's sense of presence while experiencing a VR environment. The measure consists of 14 items intended to assess various aspects of sense of presence while in VR and includes three subscales: spatial-presence, realness, and involvement. The IPQ asks participants to rate various questions on Likert scales such as “In the computer-generated world I had a sense of ‘being there’” from not at all to very much. Participants also were asked to define each instruction (e.g., look and decrease) and how difficult it was to follow the reappraisal instructions, and what percentage of time they were able to follow the instruction. Lastly, participants completed a final mDES measure of their current mood.

Timing of Mood and Emotion Ratings

Participants rated their mood at several time points. The mDES was used to measure participants' mood prior to entering the VR and at the very end of the entire experiment once they had completed other post-task individual difference measures. Mood ratings using the positive and negative scales (e.g., “1 not at all positive/negative to 9 very positive/negative”) were also collected after the three-minute VR mood induction. Emotions ratings using the positive/negative Likert scales were collected after each trial of the reappraisal task.

Data Analysis

All analyses were interpreted as significant if they crossed the $p < .05$ threshold and all follow-up t-test analyses were two-tailed.

Several pre-registered exclusion criteria were applied prior to data analysis including: lack of understanding of the task ($N = 5$), missing more than 25% of trial level data ($N = 8$). Additional participants were excluded due to a corrupted data file ($N = 1$) and mixing up the positive and negative ratings ($N = 1$). Lastly, one additional participant was excluded due to outlier scores on several measures including the VR task ratings and most individual difference measures as indicated by scores that were

greater than 3 standard deviations from the mean. This left usable data for a total of 80 participants, which reflects the desired sample indicated in our power analysis for this study (see our preregistration at the Clinical Trials website for more information).

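### Baseline mood (mDES) is collected before VR exposure but given no analysis use in this document; adjusting the between-context comparisons for it is an optional, cheap and probably modest gain in precision

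*Combined protocol and SAP*

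**What the plan says.** **Baseline.** Under Baseline and Post-Experiment Mood Ratings: "Before putting on the VR headset and at the end of the experiment, participants used the modified Differential Emotions Scale". The instrument has ten positive and ten negative items, each rated 1 to 5, and the scoring is defined: "Scales are comprised of summing all positive scores together and all negative scores together". Timing of Mood and Emotion Ratings confirms that the first administration precedes entry to the VR.

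**Mood after induction.** Under Post Mood Induction Mood Ratings: "After the three minutes of exploring the VR environment, a mood rating scale appeared in front of the participants". These are one positive and one negative item on a 1-9 scale. Timing of Mood and Emotion Ratings places them only after exposure: they "were also collected after the three-minute VR mood induction". No 1-9 mood rating before exposure is described.

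**Task ratings and design.** Under Reappraisal Task and Emotion Ratings: "For analyses the positive and negative ratings were (separately) averaged within each trial type for each participant". The design is a 3×2 "mixed factorial design: positive mood context: look-negative, look-neutral, decrease-negative", with the same three trial types in the neutral context. Allocation was random: "participants were randomly assigned both to the positive or neutral VR mood context as well as image set".

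**Analysis.** Data Analysis gives a 5% significance threshold, two-tailed follow-up t-tests, the exclusions and a final sample of 80. It writes out no model for any outcome. It names no covariate, change score or balance check, and no other use of the baseline mDES. For the power analysis it refers to a preregistration.

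**The concern.** Two comparisons implied by the design set one group of people against another: the post-induction mood ratings by context, and the context main effect on the task ratings. The document names neither as the primary test. With 80 people in total, differences between people in starting mood add noise to both. The 1-9 mood items have no baseline on their own scale, so the baseline mDES is the only pre-exposure mood measure described that could absorb some of that noise. It was collected and scored, and then given no stated use. At stake is precision only.

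**Working it through.** **Inputs from the document.** Analysed sample 80; threshold 0.05; two-tailed follow-up tests; random assignment to context between participants.

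**Assumptions, because the document gives no figure.** 40 per context; true standardised difference d; correlation r between the baseline subscale and the outcome within context.

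**The plan's own figure.** The sample of 80 is said to match the power analysis, but no effect size, SD, power or allocation ratio is given here, so it cannot be reproduced. As a substitute, the difference detectable with 80% power, unadjusted, at 40:40 is (1.96 + 0.842) × sqrt(2/40) = 0.626 SD, or 0.634 SD by noncentral t. A 35:45 split gives 0.639 SD.

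**Step 1: variance after adjustment.** One covariate multiplies the residual variance by 1 − r². Estimating its slope costs a factor 1 + 1/(80 − 1 − 3) = 1 + 1/76 = 1.013. The net variance ratio is (1 − r²) × 77/76, and its square root is the standard error ratio.

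**Step 2: power.** Noncentrality = d / sqrt[(1/40 + 1/40) × net variance ratio], with 77 degrees of freedom (78 unadjusted, variance ratio 1). At d = 0.5 the unadjusted noncentrality is 0.5/sqrt(0.05) = 2.236.

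| r | Net variance ratio | SE ratio | Equivalent N (80 / variance ratio) | Power at d = 0.5 |
|---|---|---|---|---|
| unadjusted | 1 | 1 | 80 | 59.8% |
| 0 | 1.013 | 1.007 | 79.0 | 59.2% |
| 0.1 | 1.003 | 1.002 | 79.8 | 59.7% |
| 0.2 | 0.973 | 0.986 | 82.3 | 61.0% |
| 0.3 | 0.922 | 0.960 | 86.8 | 63.3% |
| 0.4 | 0.851 | 0.923 | 94.0 | 66.8% |
| 0.5 | 0.760 | 0.872 | 105.3 | 71.7% |

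The net standard error falls by 1.4% at r = 0.2 and 4.0% at r = 0.3.

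**Step 3: break-even.** Setting (1 − r²) × 77/76 = 1 gives r = sqrt(1/77) = 0.114. Below that, adjustment costs slightly more than it returns.

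**Step 4: other effect sizes, same formula.** Power unadjusted, then adjusted at r = 0.2 and 0.3:
- d = 0.3: 26.3%, 26.9%, 28.1%
- d = 0.8: 94.2%, 94.8%, 95.7%
- d = 1.0: 99.3%, 99.4%, 99.6%

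A large induction effect is possible, since the document says of the scenes: "which were shown to elicit incidental positive and neutral states respectively in our previous studies". The gain on the mood check would then be under 2 points.

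**Step 5: context main effect on task ratings, by simulation.** 10,000 runs per setting, three trial-type means intercorrelated 0.5 (assumed), d = 0.5. Power rose from 59.4% to 61.8% when each cell correlated 0.2 with baseline, and from 59.5% to 64.9% at 0.3. Averaging three cells leaves variance (1 + 2 × 0.5)/3 = 2/3, so the averaged rating correlates r/sqrt(2/3) with baseline: 0.24 and 0.37. The gains belong to those correlations. With no true effect, type I error was 0.050 unadjusted and 0.051 adjusted at 0.2, and 0.049 for both at 0.3.

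**Step 6: context by trial type.** For a difference between two trial types with equal SDs, cell correlations r1 and r2 with baseline, and intercorrelation ρ, the correlation of baseline with the difference is (r1 − r2)/sqrt(2(1 − ρ)). It is 0 when r1 = r2. With 0.3 and 0.2 it is 0.10 at ρ = 0.5 and 0.13 at ρ = 0.7, close to break-even. Simulated power for context by (decrease-negative minus look-negative) did not improve: 59.7% to 58.9% at r = 0.2, and 60.5% to 59.9% at r = 0.3.

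**The case against.** The strongest reply is that this describes no defect. A randomised comparison does not need a covariate, and preferring ANCOVA is a matter of efficiency. That stands, and it is why the point is optional.

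Three further objections limit its weight:
- Data Analysis writes out no model at all, so the silence on covariates is weak evidence of what was done. The preregistration may assign the baseline mDES a role. A before-and-after comparison with the end-of-session mDES is also possible, though not stated.
- The document is retrospective, with exclusions counted and the sample final. Unless preregistered, adjusted models cannot be confirmatory or recover planned power.
- The correlation is unknown. A sum of ten 1-5 items would have to predict a single 1-9 item after a manipulation, or ratings of response to pictures. The document itself separates mood from stimulus-driven emotion. A low r is plausible, and at 0.1 or below nothing is gained.

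Stronger readings are tempting. A reader might infer that the unadjusted comparisons are biased by unequal starting mood. They are not: a chance baseline difference has a 95% range of ±1.96 × sqrt(2/40) = ±0.44 baseline SD, which shifts the outcome by only ±0.09 SD at r = 0.2 or ±0.13 SD at r = 0.3, and the unadjusted standard error already covers it. A reader might infer that the baseline was never analysed; the document supports only that no use is stated here. A reader might also expect a gain for the interaction that the factorial design is built to examine; the working shows none.

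What survives is a small possible gain on two between-person comparisons, from data already held.

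**Conclusion.** The point holds as an optional, low-cost improvement in precision. A pre-exposure mood measure is collected and scored, and this document gives it no analysis use. At 40 per context and d = 0.5, adjustment adds about 1 to 7 power points for r between 0.2 and 0.4 (59.8% to between 61.0% and 66.8%), more only if r reaches 0.5, and loses about 0.6 point if r is 0. The size rests on assumed values of r, d and the arm split. The gain is confined to the post-induction mood ratings and the context main effect on task ratings. The validity of the unadjusted comparison is not in question.

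**What to change.** 1. Analyse the post-induction positive and negative ratings by ANCOVA on context plus the matching baseline mDES subscale. Use only the baseline administration, because the end-of-session one follows exposure.
2. In the models for positive and negative task ratings, add the matching subscale as a between-person main effect for the test of context. Leave the trial-type and context-by-trial-type tests unchanged.
3. Report the adjusted results beside the unadjusted ones, labelled as post hoc sensitivity analyses unless the preregistration specified them. Do not use them to choose whichever result is significant.
4. If the preregistration already gives the baseline mDES a role, a sentence saying so in Data Analysis settles the point.

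The cost is four extra models (two post-induction ratings, two task-rating valences), one degree of freedom each, with no new data and a slight loss of power if baseline mood turns out not to predict the outcome.
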